The present research group previously developed and evaluated a lifestyle change program focused on obesity prevention in Mexican schoolchildren in a face-to-face format, where positive results were obtained.²² Given the current situation due to COVID-19, this program was adapted to an online format to evaluate its effect through a pilot randomized controlled trial.

Explanation for the choice of comparators

The control group will be of children from the same public school as the children in the intervention group. The risk of contamination is reduced by not having face-to-face classes, but it is not completely eliminated, since there may be participants who take classes in the same group and interact online. Even so, the results will be valid if significant differences between groups are observed, as we observed in a previous study, because the previous situation would reduce the effect of the intervention.

OBJECTIVES

Primary objective

- To evaluate the effect of an online lifestyle intervention on the BMI Z-score of Mexican schoolchildren at 4 months during the COVID-19 pandemic in the intervention group compared to a control group.

Secondary objectives

- To evaluate the effect of an online lifestyle change intervention on waist circumference, body fat, physical activity and sedentary behaviors, food consumption, nutrition knowledge and quality of life of Mexican schoolchildren at 4 months during the COVID-19 pandemic in the intervention group compared to a control group.

- To evaluate the effect of an online lifestyle intervention on the retention, participation and acceptance of Mexican schoolchildren at 4 months during the COVID-19 pandemic in the intervention group.

MATERIAL AND METHODS

Study design

This is a pilot randomized controlled trial blinded to assessors, with 4-month follow-up. It is a pilot study, because we want to evaluate the effect and feasibility of the online intervention, to later carry out a definitive study considering an adequate sample size. The study will consist of two parallel arms, of superiority and with 1:1 allocation ratio.

To carry out this protocol, the SPIRIT 2013 guidewas followed.²³ The protocol was approved by the Research Ethics Committee of the Nursing Department of the University of Sonora (CEI-ENFERMERIA-EPM-003-2020) and registered on the Clinical.trials.gov platform (NCT04772859).

Participants

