The program will center on establishing health-related goals such as increasing consumption of fruits and vegetables, increasing physical activity time, decreasing hours spent in front of a screen, and reducing consumption of sweetened beverages. The program also will include the use of self-monitoring and positive reinforcement.

Physical activity sessions: Classes will be implemented 3 days a week for 30 minutes each. Children will work on developing different skills such as: flexibility, strength, elasticity and resistance. The Zoom digital platform will be used for the online (live) sessions. The classes will be recorded, in case the children want to do a class later.

Parent's participation: Parents who agree to participate in the program will be given a user to access a web page (www.salud-nutricional.com), where children's activities will be uploaded. This will be used to upload nutrition information, parenting activities, and study questionnaires. A private Facebook group will be created to upload teaching material (videos, infographics, messages and images) on a weekly basis. The difference between using the website and Facebook is that on the page the participants will be able to have the information ordered, upload their activities and study questionnaires. The topics addressed each week will be the same as those seen with the children in the nutrition sessions. On Facebook, they will have spaces for comments, questions, feedback and social support.

Control group: The control group will receive general nutrition recommendations at the beginning of the program, based on the Nutrition and Physical Activity Guidelines in the Context of Overweight and Obesity in Mexican Population.²⁴ A digital brochure will be sent in online format to the mail or through the WhatsApp application to parents. Upon completion of the study, they will be offered access to the materials from all the onlie lifestyle sessions, as well as physical activity videos for children recorded by the physical activity team.

Outcomes

The primary outcome is the change of the BMI Z-score from baseline to 4 months between the intervention group and the control group. The change in BMI Z-score for each individual will be obtained by subtracting the BMI Z-score value at 4 months minus the baseline value. The difference between groups will be obtained by subtracting the mean of the change in the intervention group minus that of the control.

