Secondary outcomes will include the differences in waist circumference, body fat and relative fat mass, physical activity and sedentary lifestyle, quality of life, participation, attendance and nutrition knowledge. The categorical variables such as: food consumption and acceptance, will be evaluated with differences in proportions.

Recruitment

To invite the participants, school directors will first be contacted to invite them, inform them about the objectives and activities of the intervention. Fourth, fifth and sixth grade students from a public elementary school in Hermosillo, Sonora, Mexico will be invited to participate. It will seek to have a space in the students' online school classes, where parents will be invited to attend. A small presentation will be made with the invitation, objectives and activities of the intervention. During the same meeting, they will be sent via chat the link to a web page where they can find the the consent and informed assent and a personal data questionnaire to evaluate inclusion and exclusion criteria. They must be read and signed by parents and children online. Children may participate, even if the parents decide not to get involved in their part of the intervention.

Randomization

The measurements of the study will be carried out in a period of 2 weeks. Once the measurements are completed, the participants who meet the inclusion/exclusion criteria will be randomized to one of two groups: the “online lifestyle intervention” group or the control group. An independent person of the recruitment and

intervention of the study will receive a database, only with the codes and the basic variables of the study (BMI Z-score, sex and age) to perform the allocation of the participants. This will be based on a random block sequence, stratified by BMI Z-score and sex, with an allocation ratio of 1:1. The random number sequence will be generated using the randomization software available on the website: <https://randomizer.org/>. Since the assignment will be made in a single moment and without the knowledge of the participants, its concealment will be guaranteed. Participants will be explicitly informed to the assigned group.

Outcome measures

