- **Food consumption:** Some questions from the semi-quantitative food frequency questionnaire from the National Health and Nutrition Survey were used.³⁰ We asked about the frequency of consumption of ultra-processed foods (sweet beverages, fried foods, cakes and cookies) and healthy foods (fruits, vegetables and water) in the previous 7 days. For each food, the size of the portion consumed was asked, considering an average portion established in the FFQ.
- **Physical activity and sedentary activities:** The physical activity and sedentary lifestyle part of the questionnaire “The Health Behavior in School-aged Children” (HBSC) was used, which is a validated lifestyle questionnaire for school-age children.³¹ It consists of 9 questions, 5 questions related to the time and frequency of physical activity and 4 to sedentary activities.
- **Nutrition knowledge:** a questionnaire designed by the research team (not validated) was used to assess the knowledge on nutrition and health. It consists of 32 questions with multiple choice answers. The results were evaluated on a scale from 0 to 10, the more correct answers, the greater score.

- **Quality of life:** The PedsQL™ (Pediatric Quality of Life Inventory) questionnaire was used, which was designed to assess quality of life aspects in both healthy pediatric patients (2 to 18 years old) and those with chronic diseases. The questionnaire consists of 23 questions about physical, emotional, social and school functioning. The responses are on a 5-point likert scale (never = 0 to always = 4). The score for each item is reversed and transformed to a linear scale of 0–100, with a higher score indicating a better quality of life.³²
- **Retention:** It will be evaluated with the percentage of participants (intervention and control group) who complete the intervention and the measurements at 4 months.
- **Participation or attendance of schoolchildren:** It will be evaluated with the percentage of attended intervention sessions and with the percentage of participants who attended all sessions.
- **Parent's participation:** At the end of the study, parents will be asked through an online questionnaire, the number of materials consulted from the program and will be reported as a percentage.
- **Acceptance.** Acceptability will be obtained with a questionnaire applied to children and parents to qualify the intervention, materials and benefits obtained with the intervention.

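### Does the retention definition mix programme adherence with follow-up, and are participation, attendance and acceptance wrongly listed as between-arm differences?

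*Combined protocol and SAP*

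**What the plan says.** Three places in the combined protocol and SAP describe the feasibility measures.

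- **Secondary objectives.** The second objective concerns "retention, participation and acceptance of Mexican schoolchildren at 4 months during the COVID-19 pandemic in the intervention group". Unlike the objective before it, it names no comparison with controls.
- **Outcomes.** The list of secondary outcomes introduced as differences ends with "quality of life, participation, attendance and nutrition knowledge". The next sentence says that categorical variables such as "food consumption and acceptance, will be evaluated with differences in proportions". Retention is not named there.
- **Outcome measures, Secondary outcomes.** Retention is the "percentage of participants (intervention and control group) who complete the intervention and the measurements at 4 months". Participation or attendance is assessed by the "percentage of attended intervention sessions and with the percentage of participants who attended all sessions". Acceptance comes from a "questionnaire applied to children and parents to qualify the intervention, materials and benefits obtained with the intervention"; the arm is not stated.

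Two further passages bear on how these are read. Under Control group: "The control group will receive general nutrition recommendations at the beginning of the program", and later "Upon completion of the study, they will be offered access to the materials". Under Statistical Analysis, children who leave the intervention are asked for their 4-month measurement so that it can enter the intention-to-treat analysis, and changes in secondary variables are classed as exploratory.

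**The concern.** Retention appears to require two things at once: finishing the programme and being measured. The first has no threshold, and controls have no programme to finish before the study ends. A child who drops the sessions but is measured at 4 months, a case that Statistical Analysis foresees, would have an observed primary outcome and yet count as not retained. The two arms would then be judged by different rules, and the figure could not show whether children left the programme or were lost to follow-up. Study design gives feasibility as a reason for running the pilot ahead of a definitive trial, so the distinction has some value.

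Separately, listing participation, attendance and acceptance as differences suggests a comparison with controls, who have no sessions to attend and no programme to rate during the study. These measures have no baseline either, so the word cannot mean change over time. The sections also seem to disagree on which arm each measure covers.

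**Working it through.** The plan states no retention or completion rate, so there is no figure to reproduce. The check compares the sections and then sizes the strict reading.

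**Which arm does each section cover?**

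| Measure | Secondary objectives | Outcomes | Secondary outcomes list |
|---|---|---|---|
| Retention | intervention | not named | both arms |
| Participation, attendance | intervention (participation) | listed as a difference | intervention sessions |
| Acceptance | intervention | difference in proportions | no arm named |

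No measure is in conflict across all three sections. For retention, the objective and the definition differ. For participation and attendance, the objective and the definition agree, and only the summary list under Outcomes is loose. For acceptance, the objective and that list differ; that controls have no value is inferred from what the questionnaire rates, not stated.

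**Two readings of retention.** Let n be the children randomised to an arm, m those measured at 4 months, and k those measured who did not complete the programme.

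- Stayed in the allocated condition and was measured, with leaving the sessions alone not counted as leaving the study: m/n.
- Strict: (m − k)/n. The two differ by k/n.

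The definition applies one rule to both arms, and the control condition is itself described under the heading for the study's interventions. That favours the first reading. Treating the control figure as untouched by k also needs a rule that the plan does not state, namely that controls are judged on measurement alone.

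**Size on the strict reading.** Sample size gives 50 to 70 children and Study design gives 1:1 allocation, so n is 50/2 = 25 to 70/2 = 35 per arm.

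- Per such child, intervention arm: 1/25 = 4.0 points to 1/35 = 2.9 points.
- Per such child, if one pooled percentage is meant: 1/50 = 2.0 points to 1/70 = 1.4 points.

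Illustration with assumed counts, 30 per arm and 27 measured in each (follow-up 90% in both):

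| k | Intervention arm | Pooled |
|---|---|---|
| 0 | 27/30 = 90.0% | 54/60 = 90.0% |
| 3 | 24/30 = 80.0% | 51/60 = 85.0% |
| 7 | 20/30 = 66.7% | 47/60 = 78.3% |

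Even single-arm figures are imprecise at this size: the Wilson 95% interval is 74.4% to 96.5% for 27/30 and 48.8% to 80.8% for 20/30.

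**If the strict figure were tested between arms.** Assume 90% follow-up in both arms, controls judged on measurement alone, and 75% of measured intervention children completing. The intervention arm shows 0.90 × 0.75 = 67.5% against 90%. By the normal approximation, the chance of p ≤ 0.05 is about 49% with 25 per arm and 64% with 35. The plan specifies no such test of retention.

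**Can a wrong result follow for attendance?** Its unit is the intervention session. Controls have none, so no between-arm difference can be calculated and only the intervention-arm percentage can be reported.

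**The case for a change.** The best case for amending the text is that a definition should not need a generous reading. Statistical Analysis itself treats leaving the intervention and missing the 4-month visit as separate events. The general statement that categorical variables are compared by chi-square makes no exception for process measures, and on the strict reading such a test could flag a gap between arms with identical follow-up. A definitive trial would need loss to follow-up stated apart from programme drop-out, and the amendment would need only words, with no new data.

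What stands is that completing the intervention is undefined, that the objective and the definition name different arms for retention, and that the Outcomes list is loosely drafted.

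The step from there to a distorted result does not stand. Retention is absent from the measures listed as differences. The sentence on the t-test and Mann-Whitney test concerns BMI Z-score and changes in secondary outcomes, and process measures without a baseline have no change. The information said to be lost is collected elsewhere: session attendance is its own outcome, and 4-month measurements are sought from children who leave the programme. A completion threshold could no longer be fixed before the programme, since the document is dated 10/06/2021 and the programme began in March 2021.

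**Conclusion.** No change to the plan is needed. This is a gap in wording that analysts fill sensibly: follow-up reported per arm as children measured at 4 months, and attendance, parent participation and acceptance described in the intervention arm, as the secondary objective already frames participation and acceptance.

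On the natural reading of retention the distortion is zero. On the strict reading it is 2.9 to 4.0 percentage points of intervention-arm retention per measured non-completer, and zero if there are none. The 80% and 67% figures rest on assumed counts and carry no weight as predictions. Even on the strict reading, true follow-up can be recovered from the data.

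The conclusion assumes that attendance and 4-month measurement are recorded as planned and that no between-arm test is built on a strict retention figure. Nothing in Statistical Analysis uses retention to decide which children enter the BMI Z-score comparison, so the primary conclusion is unaffected and the secondary outcomes remain exploratory.

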Children from a public elementary school in Hermosillo, Sonora will be invited to participate in the study. It is worth mentioning that this public school is not representative of all the schools in Hermosillo, Sonora. Hermosillo is a city of about 884,273 inhabitants and around of 392 public elementary schools. It is located in the state of Sonora, in northwestern Mexico. Because the program is entirely online, students who agree to participate will take the intervention from home.

Sample size

No studies of online lifestyle interventions to prevent obesity in schoolchildren during the pandemic were found to obtain the effect size and standard deviation needed to estimate the study sample size. So, we decided that it would be a pilot study of at least 50 participants and no more than 70. This was decided considering our logistical capacity, which implies measuring the response variables at home in a period of 2 weeks, in addition to being able to provide intervention, among other things. The invitation will be made to all students from fourth to sixth grade of a public school in Hermosillo Sonora.

Eligibility criteria

Sign the consent and informed assent and complete the anthropometric measurements and lifestyle questionnaires.

Inclusion criteria

- 4th, 5th and 6th grade students from the participating elementary school.
- Have access to the internet.
- Have an electronic device (eg computer, laptop, tablet or smartphone).
- Nutritional status: normal weight, overweight or obesity.

Exclusion criteria

- Have a medical condition that affects body weight.
- Taking medication that affects body weight.
- Take another intervention that affects body weight.
- Have a condition that prevents physical activity.
- Withdraw informed consent or assent.
- Have a sibling participating in the study.

Implementers

The lifestyle intervention will be implemented by a Nutritionist and two interns from the Bachelor's Degree in Physical Culture and Sports from the study team. In

addition, there will be the support of interns from the Nutritional Sciences Bachelor of the University of Sonora.

Interventions of the study

Online lifestyle intervention

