- **Personal information.** The first step for the screening of the participants consists of an online questionnaire of personal data. This will be sent at the time of the invitation to the program. Personal data of the child, internet access and electronic device, if they have a disease, if they take medications or perform extra interventions that may affect body weight will be asked. In addition, the email and education leve lof the parents will be asked.

Withdrawal of participants

Participants may withdraw from the study at any time they wish, being able to inform the reason or not.

Statistical Analysis

The normality of the data will be evaluated with the Shapiro Wilk test. Data will be presented as mean and standard deviation (mean \pm SD) or median and interquartile ranges according to their distribution. An independent samples t-test or Mann-Whitney U test will be used to analyze the difference in BMI Z-score and changes in secondary outcomes between groups. A chi-square test will be used to make comparisons on categorical variables. Two-tailed tests with $p \leq 0.05$ will be used as the criterion for statistical significance.

Data will be analyzed with an intention-to-treat analysis. If participants decide to withdraw from the intervention, they will be asked if the measurement at 4 months can be obtained to have at least the primary outcome for inclusion in the intention-to-treat analysis. If data is not obtained for any reason or subjects were excluded due to a protocol violation, they will be replaced by their baseline measurement.

Results will focus on change in the primary study variable (BMI Z-score), while changes in secondary variables and sub-analyses (sex and BMI: normal, overweight/obese) will be considered exploratory only. For data analysis, NCSS version 10 software (Number Cruncher Statistical System for Windows, Kaysville, UT, USA) will be used.

Confidentiality

Identifiable information and will be kept confidential. Each participant will be assigned a code, therefore, their identifiable information will appear with that code and not with names. Only the physical files will keep the names, which will be kept by the principal investigator of the study, in a safe place. Only the study team may have access to the database, for their purposes.

Declaration of interest

The authors did not report any potential conflicts of interest.

REFERENCES

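### No listed screening item explicitly covers the physical activity exclusion, and a child found ineligible after randomisation could have a measurable outcome replaced by baseline

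*Combined protocol and SAP*

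**What the plan says.** All places are in the combined protocol and SAP.

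- **Exclusion criteria.** "Have a condition that prevents physical activity" is a criterion of its own. It stands beside three weight-related ones: "Have a medical condition that affects body weight", medication, and another intervention. The same list also contains withdrawal of consent or assent, and having a sibling in the study.
- **Recruitment.** Families receive a link to the consent and assent forms and to "a personal data questionnaire to evaluate inclusion and exclusion criteria".
- **Outcome measures, Personal information.** "The first step for the screening of the participants consists of an online questionnaire of personal data". Its described content is the child's personal data, internet access and device, the parents' email and education, and three health matters: "if they have a disease, if they take medications or perform extra interventions that may affect body weight will be asked".
- **Randomization.** After the baseline measurements, "the participants who meet the inclusion/exclusion criteria will be randomized to one of two groups". The person who allocates receives only codes, BMI Z-score, sex and age.
- **Physical activity sessions.** The intervention arm has 30-minute classes three days a week over Zoom. "The classes will be recorded, in case the children want to do a class later". Under Control group, the comparison children receive a brochure at the start, and materials and videos only after the study.
- **Statistical Analysis.** The analysis is called intention-to-treat. Children who withdraw are asked for a 4-month measurement. The baseline value is substituted if data are not obtained, or if "subjects were excluded due to a protocol violation".

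**The concern.** Of the exclusions, the physical activity criterion is the one tied directly to the exercise component. If the form meant to apply the criteria does not ask about it, a child who meets it may enter and be assigned to exercise at home, partly by recording. That is a safety matter first.

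The statistical matter follows from it. Exercise classes are given to one arm only, so a missed case is more likely to be noticed there. If noticing led to exclusion, the baseline-substitution rule would act more often in one arm than in the other, for a reason linked to allocation. It could also overwrite an outcome that was available.

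**Working it through.** **Step 1: match criteria to means of checking.**

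| Criterion | Described means of checking |
|---|---|
| Internet access; electronic device | Named questionnaire items |
| Nutritional status | Baseline anthropometry |
| Medical condition affecting weight | Disease item |
| Medication affecting weight | Medication item |
| Other intervention affecting weight | Extra-intervention item |
| Condition preventing physical activity | None named; disease item covers part |
| Sibling in the study | None named; personal data or parents' email might reveal it |
| Withdrawal of consent or assent | Arises after consent; not a form item |

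The phrase about affecting body weight in "if they have a disease, if they take medications or perform extra interventions that may affect body weight will be asked" can attach to the interventions alone or to the whole series. On the first reading the disease item is general and would catch some preventing conditions. On the second it is confined to weight-related disease. On neither reading does it clearly reach an injury or a disability that a parent would not call a disease.

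**Step 2: look for another check before randomisation.** The home visit is described as anthropometry done in under 15 minutes. The HBSC items ask about time and frequency of activity and sedentary behaviour. The PedsQL has a physical functioning domain. Both questionnaires are outcome measures, and neither is given an eligibility threshold or a person to review it. The allocator's data set has no health variable.

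**Step 3: what happens after randomisation.** The substitution rule joins its two triggers by "or": data not obtained, or exclusion for a protocol violation. As worded, the second applies whether or not a 4-month value could be measured. Protocol violation is not defined. Because the exclusion list includes withdrawal of consent, which can occur after allocation, exclusion after randomisation is foreseeable.

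**Step 4: weight of one substituted child.** The plan has 50 to 70 participants allocated 1:1, so n = 25 to 35 per arm. If a child's true change is d and it is set to 0, the arm's mean change moves by −d/n. The child's weight is 1/35 = 2.9% to 1/25 = 4.0% of the arm mean.

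**Step 5: how many children (illustration only).** The documents give no prevalence. Assume that p = 0.5% to 5% of otherwise eligible children have such a condition and that none is screened out. The expected number is N × p, and the chance of at least one is 1 − (1 − p)^n.

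| | p = 0.5% | p = 5% |
|---|---|---|
| Expected, N = 50 | 0.25 | 2.5 |
| Expected, N = 70 | 0.35 | 3.5 |
| At least one in the trial, N = 50 | 22% | 92% |
| At least one in the trial, N = 70 | 30% | 97% |
| At least one in the intervention arm, n = 25 | 12% | 72% |
| At least one in the intervention arm, n = 35 | 16% | 83% |

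If every such child in the intervention arm were found and excluded, the expected share of that arm's mean replaced by zeros would be n × p × (1/n) = p, that is 0.5% to 5%. The plan has no figure of its own to reproduce here, since its sample size is a logistical choice.

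**The case against.** A reader might infer that the questionnaire definitely does not ask about this exclusion. The documents do not support that. The Personal information entry is a short description, not the form itself. It also omits the sibling exclusion, which suggests a summary. Recruitment says that the form evaluates the criteria without carving any out, and Randomization admits only children who meet them. The form is called the first screening step, so a later one is not ruled out. Parents also see a presentation of the activities before consenting and could raise an obvious barrier. All of this stands, and it limits the finding to what is explicitly described. It does not close the gap, because no later eligibility step is described and a rule that admits only eligible children works only if each criterion is ascertained.

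A reader might also infer that missed children would be discovered only in the intervention arm. Both arms have home visits and complete the HBSC and PedsQL, and any of these could reveal such a condition. The most that can be said is that discovery is more ready where classes are held.

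The bias argument is also a chain: a missed child, noticed, classed as a violation, then excluded. No section says that ineligibility counts as a violation or requires exclusion on discovery. That is fair, and it is why little weight rests on size. The wording of the substitution rule is nonetheless a defect however often it is used.

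Finally, the document is dated 10/06/2021 while the programme runs from March to July 2021, so the form may already have been used.

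**Conclusion.** The point holds in limited form. The listed items do not explicitly cover one stated exclusion, the form that contains them is the named means of applying the criteria, and no other step before randomisation is assigned to that check. The disease item gives partial cover. The stronger ground is safety: a named safeguard has no stated means of application.

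The second part also holds. Substituting baseline for a child excluded as a protocol violation, even when the 4-month value could be measured, conflicts with the stated intention-to-treat analysis. Each such child carries 2.9% to 4.0% of the arm's mean change. With an assumed prevalence of 0.5% to 5% and no screening, 0.25 to 3.5 children are expected in the whole trial, so there may be none. The effect on the primary result is probably small, and a claim of material bias is not supported.

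**What to change.** 1. Reconcile Exclusion criteria, Recruitment and Personal information. Add to the questionnaire completed before randomisation one direct item, answered by a parent and worded as the existing criterion, without widening it. If enrolment is already complete, state how this exclusion was in fact ascertained and carry the item into the definitive study.
2. In Statistical Analysis, state that a child found ineligible after randomisation, in either arm, stays in the randomised arm and is analysed with the measured 4-month value, and that baseline substitution is not applied to a child whose 4-month value is measured.

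Decisions about such a child's further class participation are for the investigator.

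The cost is one extra item on an existing online form and a sentence or two of text. A few children may be screened out before randomisation.
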